#### **4.2.2 Performance Measures**

- Change in 6 Minute Walking Test (6MWT) from Baseline to D90
  - The primary estimand for this outcome is the difference in mean 6MWT change from baseline.
  - This continuous outcome will be analyzed as described in [Section 3.5](#), i.e. using a mixed effect model for repeated measurements.
- Change in Active Stand Test from Baseline to D90

- The primary estimand for this outcome is the relative proportion with postural orthostatic tachycardia syndrome by the stand test.
  - This binary outcome will be analyzed as described in [Section 3.3](#), i.e. using a GEE model.
- Change in Neurocognition Index (NCI) standard score from the CNS-VS from Baseline to D90
  - The primary estimand for this outcome is the difference in mean change in the NCI standard score from the CNS-VS from baseline.
  - This continuous outcome will be analyzed as described in [Section 3.5](#), i.e. using a mixed effect model for repeated measurements.

#### **4.2.3 Laboratory Measures**

- Change from Baseline to D90 in CRP, ESR, D-Dimer, and Fibrinogen
  - The primary estimand for these outcomes is the difference in mean change from baseline.
  - These continuous outcomes will be analyzed as described in [Section 3.5](#), i.e. using a mixed effect model for repeated measurements.

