## **15.4 Analysis of Secondary Endpoints**

The key secondary outcome will be the change in the PROMIS-29 score from baseline to D90. This will be analyzed from the mITT population using a linear regression model for follow-up PROMIS-29 with terms for the baseline value, randomized treatment and randomization strata (<6 months v.  $\geq$  6 months of symptoms) – an analysis of covariance model (ANCOVA) and tested using a two-sided 0.05 level test.

Continuous secondary events (e.g., IL-6) will be compared using the ANCOVA approach. Antigen detection will be summarized by proportion with 95% Clopper-Pearson confidence intervals and will be compared using a two-sided 0.05 level Fisher exact test.

As above, eligibility is determined by Long COVID attributed to a SARS-CoV-2 infection prior to August 15, 2022. All participants will be required to have Long COVID attributed to an infection prior to this date. A sub-analysis will address individuals with and without a known history of SARS-CoV-2 re-infection after August 15, 2022.

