## **15.6 Sample Size and Randomization**

This is an exploratory study, and the primary results will be descriptive. We will use AER002 as a probe to better understand LC biology and determine whether a signal is present to warrant further study.

The study will enroll 30 participants who meet the WHO LC criteria. Participants will be enrolled at a single center and randomized 2:1 to receive AER002 1200mg or placebo. Randomization will be stratified by duration of infection (<6 months and  $\geq$  6 months) at Day 0.

For PROMIS-29, assuming a standard deviation (SD) of the within-person difference of 10, then the planned sample size will have 80% power to detect a difference of 11.2 on a two-sided 0.05 level test.

For biomarkers, such as IL-6, we will be able to detect a difference from a mean value of 2.5 pg/mL to 1.1 times the within-person standard deviation with 80% power.

We assume that 25% of participants will have positive antigen at entry, we will have 62% power to detect a reduction to < 1% with positive antigen on the treatment arm.

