### 2.2. Study Endpoints

#### Efficacy Endpoints

- The change in PROMIS-29 Physical Health and Mental Health summary scores comparing Baseline to D90.
- Change in other assessments (EuroQoL Quality of Life, CNS Vital Signs, DASI, COMPASS-31, WHO-DAS 2.0, PGIC, ECog-39, dysautonomia (COMPASS-31), DSQ-PEM, 6 Minute Walking Test, Active Stand Test performance) between Baseline and at D30, D90, D180, and D360.

- Percentage of participants with no detection of SARS-CoV-2 plasma remnants (i.e., viral detection by reverse transcriptase-polymerase chain reaction (RT-PCR) and Spike protein fragments) comparing baseline to D30, D90, D180, and D360.
- Proportion with reduction in inflammatory markers (e.g., interleukin-6 (IL-6), C-reactive protein (CRP) at Baseline and at D30, D90, D180, and D360.

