### **2.4. Sample Size and Study Power**

This is an exploratory study, and the primary results are meant to be descriptive. We use AER002 as a probe to better understand LC biology and determine whether a signal is present to warrant further study.

The study planned at least 30 participants who meet the WHO LC criteria. Participants are enrolled at a single center and randomized 2:1 to receive AER002 1200 mg or placebo.

For PROMIS-29, assuming a standard deviation (SD) of the within-person difference of 10, then the planned sample size has 80% power to detect a difference of 11.2 on a two-sided 0.05 level test.

For biomarkers, such as IL-6, we can detect a difference from a mean value of 2.5 pg/mL to 1.1 times the within-person standard deviation with 80% power.

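### SAP Section 4 plans no analysis of IL-6 and no efficacy analysis at D360, although SAP 2.2 lists both, and the SAP's yes/no form for IL-6 conflicts with its own power statement

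*Combined protocol and SAP*

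**What the plan says.** - **Endpoint list (SAP 2.2).** The inflammation endpoint is "Proportion with reduction in inflammatory markers (e.g., interleukin-6 (IL-6), C-reactive protein (CRP) at Baseline and at D30, D90, D180, and D360". The other assessments are also to be compared "between Baseline and at D30, D90, D180, and D360", and plasma antigen is listed at the same four follow-up times.
- **Power (SAP 2.4, repeated from protocol 15.6).** The stated power is 80%: "For biomarkers, such as IL-6, we can detect a difference from a mean value of 2.5 pg/mL to 1.1 times the within-person standard deviation". This describes a difference in means.
- **Protocol 15.4.** "Continuous secondary events (e.g., IL-6) will be compared using the ANCOVA approach".
- **Planned analyses (SAP Section 4).** The secondary laboratory item in 4.2.3 is "Change from Baseline to D90 in CRP, ESR, D-Dimer, and Fibrinogen". The exploratory item in 4.3.3 takes the same four markers to D15, D30 and D180 and follows antigen only to D180. IL-6 is named nowhere in the section. The only follow-up times named are D15, D30, D90 and D180.
- **General methods.** SAP 3.3 allows Fisher's test or logistic regression for binary outcomes, and a Poisson GEE when they are measured repeatedly. SAP 3.5 gives ANCOVA or a mixed model for continuous outcomes and mentions log-transformation for biomarkers.

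**The concern.** The endpoint list and the analysis list of one document disagree. Followed literally, Section 4 never compares the marker that the SAP itself uses to illustrate its biomarker power, and 12-month efficacy data are collected with no comparison assigned to them. Reducing post-COVID inflammation is a secondary objective, and Appendix 1 of the protocol schedules inflammation markers at every in-person visit from Baseline to D360.

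The gap leaves a choice open. With no IL-6 analysis in Section 4, an analyst could report a mean comparison (protocol 15.4), a proportion (SAP 2.2) or nothing, and could settle this after seeing results. In a 30-person study looking for a signal, with no multiplicity adjustment for secondary endpoints (SAP 4.2), that freedom matters. If the choice fell on the SAP's own form, most of the advertised sensitivity would be lost.

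**Working it through.** **Inputs from the documents.** 20 participants on AER002 and 10 on placebo (SAP 2.1); a difference of 1.1 within-person SD with 80% power (SAP 2.4).

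**Assumptions.** Two-sided 0.05: the documents state this for PROMIS-29 ("80% power to detect a difference of 11.2 on a two-sided 0.05 level test"), and I take the same for IL-6. Changes are normally distributed, there is no dropout, and one follow-up visit is compared. The documents give no placebo reduction rate, so it is varied.

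**Step 1: the stated power as a continuous comparison.** The standard error in SD units is √(1/20 + 1/10) = √0.15 = 0.387, so the standardised effect is 1.1 / 0.387 = 2.84.
- Normal approximation: Φ(2.84 − 1.96) = Φ(0.88) = 81.1%.
- Noncentral t with 28 df: 78.3%.
- Difference detectable with 80% power: 1.085 SD (normal) or 1.124 SD (t).

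The stated 80% is reproduced. The PROMIS-29 figure of 11.2 with an SD of 10 is 1.12 SD, which agrees with the t result. Both power statements therefore fit a comparison of continuous means with 20 v 10.

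**Step 2: the same effect as reduction yes or no.** Let m be the mean fall on placebo in SD units. The proportion falling is Φ(m) on placebo and Φ(m + 1.1) on AER002. At m = 0 these are 50% and Φ(1.1) = 86.4%. Exact power is the sum, over all 21 × 11 possible tables, of the product of the two binomial probabilities for tables with p ≤ 0.05.

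| Placebo falling | AER002 falling | Fisher power | Chi-square power |
|---|---|---|---|
| 15.9% | 54.0% | 44.6% | 53.9% |
| 22.7% | 63.7% | 45.4% | 59.7% |
| 30.9% | 72.6% | 50.5% | 61.7% |
| 40.1% | 80.2% | 54.1% | 61.5% |
| 50.0% | 86.4% | 51.6% | 58.1% |
| 59.9% | 91.1% | 46.4% | 51.6% |
| 69.1% | 94.5% | 38.7% | 46.7% |

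A fine grid of m from −2.5 to 2 gives maxima of 54.1% (Fisher) and 61.8% (chi-square). Neither test reaches 80% at any placebo rate.

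**Step 3: what 80% would need in the yes/no form.** With 20 v 10 and 50% of placebo falling, Fisher's test needs a shift of about 1.65 SD. Keeping 1.1 SD and 2:1 allocation, a normal approximation needs about 18 + 36 = 54 participants (22 + 44 = 66 with continuity correction).

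**Step 4: SAP 2.2 against Section 4.**

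| Item | SAP 2.2 | SAP Section 4 |
|---|---|---|
| IL-6 | Listed, as a proportion | Absent |
| CRP | Listed in the same bullet, as a proportion | Continuous change, D15 to D180 |
| Antigen | To D360 | To D180 |
| Other assessments | To D360 | To D180 at the latest |

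**The case against.** **The low power belongs to an analysis that Section 4 does not plan.** This stands. CRP, from the same bullet of SAP 2.2, is analysed as a continuous change, and SAP 3.5 treats biomarkers as continuous. A reader might infer that the trial will test IL-6 with about 52% power; the documents do not support that. They show a conflict over the form of the endpoint, and the figures show what one of the forms would cost.

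**SAP 3.3 does not compel Fisher's test.** This also stands: logistic regression or GEE is allowed. A pooled longitudinal analysis was not calculated, and its power would depend on within-person correlation. However, the GEE in SAP 3.3 estimates the effect against the baseline visit, and an indicator of reduction from baseline has no baseline value, so that model would need adapting.

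**IL-6 is not the only powered biomarker.** A reader might infer that it is. SAP 2.4 names it only as an example, and protocol 15.6 also states 62% power for antigen.

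**The omissions may be deliberate.** Protocol Section 15 lets the SAP modify the plan, protocol 9.3.2 makes IL-6 and TNF-alpha only possible measurements, and the protocol synopsis places inflammatory markers under other evaluations. This explains why TNF-alpha need not return: SAP 2.2 already puts CRP in its place. It does not explain IL-6, which SAP 2.2 keeps, or antigen at D360, which SAP 2.2 adds beyond the protocol's six months while 4.3.3 stops at D180.

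**Methods for 12 months exist.** SAP 3.5 includes visit-by-group terms and SAP 3.6 defines a 12-month window, so it would be wrong to say that D360 has no usable method. It has no outcome assigned to it. D360 safety is covered, because the primary safety outcome runs throughout the study.

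**Conclusion.** The point holds as an internal inconsistency of the SAP with a practical consequence. Two items listed in SAP 2.2, IL-6 and the D360 comparisons, have no efficacy analysis in Section 4. The one form in which the SAP makes IL-6 an endpoint contradicts SAP 2.4 and protocol 15.4.

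At 1.1 SD with 20 v 10, the choice of form moves single-visit power from 78% to 81% down to 39% to 54% by Fisher's test over placebo reduction rates of 16% to 69%. The placebo rate is assumed, but the conclusion does not depend on its value. Baseline adjustment could raise the continuous power further.

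The study is exploratory and its primary results are descriptive, so this is a correction worth making and no threat to the primary safety analysis. A reader might also take protocol 15.4 to fix log-transformation and D90 for IL-6. It states neither; log-transformation is offered in SAP 3.5, and D90 matches the other markers in SAP 4.2.3.

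**What to change.** 1. Add IL-6 to SAP 4.2.3 (D90) and 4.3.3 (D15, D30, D180) as a continuous, baseline-adjusted outcome under SAP 3.5, log-transformed if skewed, as is already done for CRP. TNF-alpha is optional.
2. In SAP 2.2, replace the proportion form of the inflammation endpoint by mean change from baseline. Record this as a SAP modification of protocol 5.1 and the synopsis, which carry the proportion form.
3. Add D360 to the exploratory visit lists in SAP 4.3 for the outcomes measured then, and extend antigen in 4.3.3 from D180 to D360 to match 2.2.
4. If either item was dropped on purpose, remove it from SAP 2.2 and give the reason.

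The amendment should say whether it was made before any group-level results were seen, since protocol 15.5 plans an interim analysis at three months.

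The cost is SAP wording and a few extra model runs. The D360 visit and the inflammation and viral-persistence samples are already in the Schedule of Events.

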### **4.3 Exploratory Efficacy Analyses**

#### **4.3.1 Questionnaires**

- Change in PROMIS-29 score from Baseline to D15
  - The primary estimand for this outcome is the difference in mean PROMIS-29 score from baseline.
  - This continuous outcome will be analyzed as described in [Section 3.5](#), i.e. using a mixed effect model for repeated measurements.
- Change in the LIINC Questionnaire – Symptom Assessment, Duke Activity Status Index (DASI), Post-COVID Functional Status Scale, The DePaul Symptom Questionnaire (DSQ) post-exertional malaise (PEM) questionnaire, DSQ-PEM FU1, between Baseline and D15 (if measured), D30, D90, and D180
  - The primary estimand for these continuous outcomes are the difference from baseline for each respective score.
  - These continuous outcomes will be analyzed as described in [Section 3.5](#), i.e. using a mixed effect model for repeated measurements.
- Change from Baseline to D15, D30, and D180 for LIINC Questionnaire – Quality of Life, DASI, (COMPASS)-31, WHO-DAS 2.0 and ECog

- The primary estimand for these continuous outcomes are the difference from baseline for each outcome.
- These continuous outcomes will be analyzed as described in [Section 3.5](#), i.e. using a mixed effect model for repeated measurements.

#### **4.3.2 Performance Measures**

- Change from Baseline to D15 (only for 6MWT), D30, and D180 in 6 Minute Walking Test, Active Stand Test and CNS-VS.
  - The primary estimand for these outcomes is the difference in mean change from baseline.
  - These continuous outcomes will be analyzed as described in [Section 3.5](#) , i.e. using a mixed effect model for repeated measurements.

#### **4.3.3 Laboratory Measures**

- Change from Baseline to D15, D30, and D180 in CRP, ESR, D-Dimer, and Fibrinogen
  - The primary estimand for these outcomes is the difference in mean change from baseline.
  - These continuous outcomes will be analyzed as described in [Section 3.5](#) , i.e. using a mixed effect model for repeated measurements.
- Percentage of participants with no detection of SARS-CoV-2 plasma remnants (i.e., viral detection by reverse transcriptase-polymerase chain reaction (RT-PCR) and Spike protein fragments) compared to Baseline through D180.

### **5. Safety Analysis**

The primary outcome will be the number of individuals in each group experiencing a severe (Grade 3 or greater) Adverse Event (AE) attributed to be possibly, probably, or definitely related to study treatment will be compared between the arms. The number and proportion of participants treatment-emergent adverse events (TEA), serious adverse events (SEA) and Adverse Events of Special Interest (AESI) will also be summarized across treatment groups in the mITT population. Differences will be tested by a 0.05 level two-sided Fisher's exact test. Agresti and Coull confidence intervals will be calculated for proportions.

